LT	Lung or Lung or Heart Transplant
PhRMA	Pharmaceutical Research and Manufacturers Association
PASS	Post Authorization Safety Study
RR	Relative Risk
SOPs	Standard Operating Procedures
SCC	Squamous Cell Carcinomas
SAE	Serious Adverse Event
SOT	Solid Organ Transplant
UK	United Kingdom
US	United States of America

1. INTRODUCTION

Voriconazole (Vfend[®]) is approved for the treatment of invasive aspergillosis (IA) and other systemic fungal infections. In addition to the approved indications, published reports indicate that voriconazole is used as prophylaxis to prevent IA in solid organ transplant (SOT), primarily lung or lung/heart transplantation (LT) [1, 2].

Patients undergoing LT typically receive immunosuppressive medications for a period of time after the transplantation to prevent organ rejection. This prolonged immunosuppression renders these patients highly susceptible to invasive fungal infections (IFIs) such as IA [3]. As a result, antifungal prophylaxis is commonly prescribed for patients after LT in many transplant centers worldwide. Some transplant centers prefer universal antifungal prophylaxis for all patients, while others use "targeted" prophylaxis in only the highest risk patients. The data from a recent worldwide survey showed that voriconazole is the preferred antifungal for prophylaxis either as monotherapy or in combination with another antifungal agent[4]. It is important to note, however, that there have been no prospective comparative clinical trials conducted to evaluate the safety and efficacy of voriconazole prophylaxis in this clinical situation, and voriconazole has not been approved by any regulatory authority for this use.

Squamous cell carcinomas (SCC) is the second most common skin cancer in the general population after the basal cell carcinoma (BCC), and it is the most common cancer in immunocompromised patients with SOT. Overall, the incidence of SCC in SOT patients is 65 to 250 times that of the general population [5], and varies by type of organ transplant. Furthermore, SCC has been reported to be more aggressive and has been associated with a high mortality in immunocompromised patients [6]. The recognized risk factors for the development of SCC include old age, prolonged sunlight exposure, long duration of immunosuppressive therapy, infection with human papillomavirus (HPV) and lower CD4 cell counts, and certain host factors such as White race and Fitzpatrick skin types I, II, or III [7-9].

Recently, single case reports [10-12] and small case series [13-15] of SCC in patients with immunocompromised status such as patients with SOT, hematological malignancy or with human immunodeficiency virus (HIV) infection using voriconazole have been reported. Two retrospective observational studies were conducted in the US which investigated the risk of SCC during voriconazole therapy in patients with LT. In a retrospective cohort study, Feist et al. [16] reported a higher incidence of SCC and/or BCC in LT patients who received voriconazole for prophylaxis or treatment of aspergillosis compared to those who received other antifungals or no treatment (42.9% vs. 9.9%)¹. In another study, Vadnerkar et al. [17] evaluated risk factors for SCC in LT patients received voriconazole) and concluded that prolonged duration of voriconazole therapy and residence in locations with high-levels of sun exposure were independent risk factors for SCC in patients with LT receiving voriconazole. However, severe immunosuppression has been recognized as an independent risk factor for SCC in several published studies [5]. Neither Feist nor Vadnerkar adequately

¹ As of February 10, 2012, full text of Feist et al. paper is not available and the information is based on the abstract only. The study examined combined endpoint of SCC and/or BCC, and did not report separate incidence estimates for SCC and BCC.

controlled for patient immune status in their studies. It is possible that LT patients who receive voriconazole prophylaxis, particularly for longer durations, may be more immunosuppressed compared to patients who do not receive voriconazole. Therefore, the association between voriconazole use and SCC reported in these studies may be biased due to "confounding by indication."

In addition to the reports of SCC, there have been several reports of melanoma in immunocompromised patients receiving prolonged voriconazole therapy [18]. To date, there have been no published studies that have investigated the association between voriconazole use and the development of melanoma.

The potential association between voriconazole use and the development of SCC or melanoma in patients can be evaluated either by a retrospective cohort or a case-control study design. In this context, a retrospective cohort study design has several advantages over a case-control study design. A retrospective cohort study will enable us to estimate the incidence of SCC in patients who received voriconazole and compare this to the incidence in patients who did not receive voriconazole. This study design will allow us to describe a broad range of potential risk factors for SCC (demographics, comorbid conditions, concomitant medications including immunosuppressive agents) in patients who received voriconazole and compare these to patients who did not receive voriconazole. In addition, this study design will enable us to evaluate multiple endpoints (e.g., SCC and melanoma).

Based on the recently conducted comprehensive study feasibility assessment of existing EU and US databases, we concluded that an adequately powered retrospective cohort study in the overall voriconazole-treated population would not be feasible because of the low incidence of SCC^2 . However, the background incidence of SCC has been reported to be relatively high in the LT patient population, and the majority of cases of SCC reported in patients receiving voriconazole have been in LT patients. By focusing on LT patients, we will be more likely to identify a sufficient number of patients to be able to conduct an adequately powered retrospective cohort study.

A recently completed study feasibility assessment in LT centers by the Principal Investigator (PI) (See section 3.6) indicated that it is feasible to conduct a retrospective cohort study with an adequate power using data from multiple LT centers in the EU, US and Australia.

This proposed retrospective cohort study evaluating the potential association between voriconazole use and the development of SCC of skin in patients with LT is a post-authorization safety study (PASS) committed to the European Medicines Agency (EMA).

² Report submitted to the EMA on 20 September, 2010

2. STUDY OBJECTIVES

2.1. Primary objective

• To assess the potential association between voriconazole use and the development of SCC of skin in patients with lung or heart/lung transplant.

2.2. Secondary objective

• To assess the potential association between voriconazole use and the development of melanoma in patients with lung or heart/lung transplant.

3. METHODS

3.1. Study design

This will be a non-interventional observational study. The study objectives will be accomplished by means of a retrospective cohort study design.

3.2. Study population

Lung or lung/heart transplant recipients constitute the study population and will be identified from a multicenter, multinational retrospective database of patients with LT. The study database is being developed and will include retrospective patient-level data from several lung transplant centers in the EU, North America and Australia.

3.3. Definition of exposed and unexposed cohorts

Voriconazole exposed cohort: Patients with LT who receive at least one dose of voriconazole regardless whether they also receive other antifungals will be included in this cohort.

Unexposed cohort: Patients with LT who did not receive voriconazole will be included in this cohort.

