3.9.1. Voriconazole and other antifungal treatment

Data on voriconazole therapy will include:

- Indication:
 - o Prophylaxis of IFIs
 - o Treatment of IFIs
- Dose and frequency
- Duration of therapy (will be calculated by using the treatment start and stop dates)

Data on antifungl agents other than voricoanzole (e.g., itraconazole, posaconazole, amphotericin B) will also be collected.

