7. STATISTICAL ANALYSES

Detailed statistical analyses is outlined in the statistical analysis plan (SAP). Briefly, the following analyses will be conducted.

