7.3.1. Analyses to address primary objective

Comparison of voriconazole exposed cohort and unexposed cohort: A univariate Cox proportional hazard regression analysis will be conducted to assess the association between voriconazole and SCC of skin. Based on the results of the univariate analysis, a multivariate Cox proportional hazard regression model will be developed to evaluate the independent effect of voriconazole use on the risk of SCC of skin while controlling for effects of major confounding variables such as exposure to sunlight (using geographical location of residence as a proxy variable), immune status (using immunosuppressive medications as a proxy variable) and confounding by indication (using underlying medical conditions as a proxy variable). In addition to multivariate regression analyses, other analytic methods will be considered in order to control for major confounders such as patients' immune status and exposure to sunlight.

Further, depending on the number of patients, subgroup analyses such as comparison of patients who receive voriconazole but no other antifungals (i.e., 'voriconazole only cohort') with patients who did not receive voriconazole (i.e., unexposed cohort) will be considered to assess the association between voriconazole and SCC of skin.

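### Exposure is one dose versus none, and no analysis named in the protocol uses duration, although the protocol cites prolonged use as a reported risk factor and collects the dates

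*Protocol*

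**What the plan says.** **Exposure.** Protocol 3.3 counts as exposed "Patients with LT who receive at least one dose of voriconazole", whether or not another antifungal was given as well. The unexposed cohort is everyone who had no voriconazole. There is no minimum course length and no lag.

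**Background.** Section 1 reports that in one of two cited observational studies "prolonged duration of voriconazole therapy and residence in locations with high-levels of sun exposure were independent risk factors for SCC". The same section then cautions that "LT patients who receive voriconazole prophylaxis, particularly for longer durations, may be more immunosuppressed compared to patients who do not receive voriconazole".

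**Data.** Section 3.9.1 collects indication (prophylaxis or treatment), dose and frequency, and also "Duration of therapy (will be calculated by using the treatment start and stop dates".

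**Analysis.** Section 7.2 gives incidence by exposed and unexposed cohort, with a list of twelve example stratification variables. Section 7.3.1 compares the two cohorts: "A univariate Cox proportional hazard regression analysis will be conducted to assess the association between voriconazole and SCC of skin". A multivariate Cox model follows, and a voriconazole-only subgroup is to be considered. Section 7.3.2 takes the same approach for melanoma. No duration, cumulative-dose or time-dependent exposure term is named in any of these. Section 7 opens by referring the detail to a separate statistical analysis plan (SAP).

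**Planning.** Section 3.8 and Appendix 1 require 157 exposed and 314 unexposed patients for RR 2.5, with 5% incidence in the unexposed, a 1:2 ratio, 80% power and two-sided 5% alpha. Appendix 1 defines the RR as that of the exposed cohort against the unexposed cohort.

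**The concern.** Under 3.3, a patient given one dose and a patient treated for years enter the model with the same exposure value. An SCC found days after a first dose counts as a voriconazole event on the same footing as one found after long therapy. Because voriconazole is recorded for both prophylaxis and treatment, course length may vary widely within the exposed cohort.

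If risk rises with duration, patients with short courses carry little of it and draw the ever/never hazard ratio toward 1. For a post-authorisation safety study the harmful error is a reassuring result, and dilution pushes that way. The named analyses would also leave unexamined a signal that the protocol itself cites. Of the seven case-report, case-series and melanoma references (10 to 15 and 18), six have prolonged or long-term use in their titles.

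**Working it through.** **Step 1: reproduce the plan's figure.** Inputs from 3.8 and Appendix 1: p0 = 0.05, RR = 2.5 so p1 = 0.125, k = 2 unexposed per exposed, two-sided alpha 0.05, power 80%.

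Formula (two proportions, pooled variance under the null, no continuity correction):

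n(exposed) = [1.960·√(p̄(1−p̄)(1+1/k)) + 0.842·√(p1(1−p1) + p0(1−p0)/k)]² / (p1−p0)²

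- p̄ = (0.125 + 2×0.05)/3 = 0.075
- first root = √(0.075×0.925×1.5) = 0.3226
- second root = √(0.125×0.875 + 0.05×0.95/2) = 0.3649
- n = [(1.960×0.3226 + 0.842×0.3649)/0.075]² = 156.9, so 157 exposed and 314 unexposed

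This matches the stated size, and power at 157/314 is 80.0%. Of the 72 exposed-cohort sizes in Table 1, 36 were checked (p0 of 3, 5, 10 and 15%) and each agrees within one patient.

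**Step 2: what the 2.5 refers to.** Appendix 1 defines it over the whole exposed cohort. On that definition it is already an average over short and long courses, so nothing is to be deducted from the 80%.

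**Step 3: what would follow on a different reading.** Suppose instead that 2.5 held only for prolonged users and that a share f of the exposed cohort had RR 1. Neither supposition is in the protocol. Then

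RR(ever/never) = (1−f)×2.5 + f×1, and p1 = 0.05 × RR.

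| Assumed f | Ever/never RR | Power at 157/314 | Sizes for 80% power |
|---|---|---|---|
| 0% | 2.50 | 80% | 157/314 |
| 10% | 2.35 | 73% | 187/374 |
| 20% | 2.20 | 66% | 229/458 |
| 30% | 2.05 | 57% | 287/574 |
| 40% | 1.90 | 47% | 375/750 |
| 50% | 1.75 | 37% | 517/1034 |

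The protocol's Table 1 shows the same sensitivity. At p0 = 5% and 1:2, moving from RR 2.5 to 2.0 raises the requirement from 157/314 to 312/624. In the formula above, RR 2.0 corresponds to f = 0.5/1.5, or one third.

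**Step 4: what cannot be computed.** The protocol gives no distribution of course lengths and no dose-response. The power of a duration analysis, and the actual amount of dilution, are therefore unknown.

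**The case against.** Four stronger readings are tempting, and the protocol does not support them.

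- **That the stated power is lost.** A reader might infer this from the table above. The planning RR is defined for the whole exposed cohort, and 157/314 reproduces at 80% for that contrast. The one comparative figure cited in section 1 (42.9% against 9.9%, ratio about 4.3, for SCC and basal cell carcinoma combined) compares recipients with non-recipients, with no duration threshold mentioned. It gives no ground for treating 2.5 as an effect of prolonged use only. Table 1 also already tabulates RR 2.0.
- **That the study will never use duration.** The protocol says "Detailed statistical analyses is outlined in the statistical analysis plan (SAP"), and that plan is not to hand. Collecting start and stop dates suggests some intended use. The point is limited to what the protocol names.
- **That prolonged use is the study's own hypothesis.** Sections 2.1 and 2.2 set the objective as voriconazole use, without qualification. The ever/never contrast answers that objective directly.
- **That a duration analysis would separate drug effect from confounding by indication.** Section 1 warns that longer users may be more immunosuppressed, so a gradient could arise from the same confounding.

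One part of the deferral argument does not carry. Section 7 is a summary, but it is specific where it chooses to be: it lists strata down to occupation and neutropenia episodes and names a voriconazole-only subgroup. The collapse to ever/never is made in 3.3 itself and is not left to the SAP.

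**Conclusion.** The point holds in a limited form and is worth acting on. The protocol fixes a one-dose-or-none exposure and names only analyses of that contrast, while citing a duration signal and collecting the data to examine it. If risk depends on duration, the primary estimate is biased toward 1 by an amount that the protocol does not allow one to calculate.

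The sample size itself is sound as written. The figures of 66% and 47% are illustrations. They need an assumed share of no-effect courses (20% and 40%) and a reading of RR 2.5 that the protocol does not give. What is open on the planning side is narrower: no reason is offered why 2.5 should hold as an average over all course lengths.

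**What to change.** **In 7.3.1**, pre-specify beside the ever/never contrast an exposure-response Cox analysis. Voriconazole duration accrued to date enters as a time-dependent covariate, lagged, with adjustment for immunosuppression and the other confounders already named there. Show the result also in duration bands with zero exposure as reference. Fix the functional form, band limits and lag before analysis, so that cut-points are not chosen from the data. If the SAP already contains such an analysis, a sentence in 7.3.1 pointing to it is enough.

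**In 3.8**, state that the planning RR is an average over all durations of use, and refer to the smaller RRs in Table 1 as the sensitivity range.

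**Cost.** Wording and a little more analysis work; the dates are already collected. Form and lag must be chosen in advance, and a poor choice (for example a linear term where risk has a threshold) could misdescribe the relation, which is why the bands are shown too. The report should say that a gradient would not by itself rule out confounding by indication.

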3.4. Inclusion and exclusion criteria

Inclusion criteria

- Patient aged \geq 18 years at the time of LT
- Patient received LT between 1 January, 2005 and 31 December, 2008

Exclusion criteria

• Patient with simultaneous or sequential abdominal organ transplant (Note. Bone marrow transplant recipients who undergo LT will not be excluded)

Figure 1. Eligibility in the study assessing the potential association between voriconazole use and SCC of skin and melanoma in patients with LT

3.5. Index date and follow up

The index date will be the "date of LT". The study eligible patients will be followed from the index date to whichever of the following occurs first:

- Occurrence of SCC of skin or melanoma (follow up will be continued for the occurrence of a second endpoint if the patient develop one endpoint)
- Death
- Last patient visit or 31 December, 2012, at which time all surviving patients will be censored, whichever occurs first.

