7.2. Incidence estimates

Incidence rates of SCC of skin and melanoma by voriconazole exposed cohort and unexposed cohort will be calculated. Patients with a history of SCC will be excluded, when estimating the SCC incidence, and patients with a history of melanoma will be excluded when estimating the melanoma incidence.

The incidence estimates will be stratified by selected variables such as:

• Age at transplant

- Gender
- Race/ethnicity
- Occupation
- Skin phototype
- Geographical location
- Exposure to sunlight
- Reason for transplant
- Co-morbid conditions
- Immunosuppressive agents used
- Number of transplant rejection episodes
- Number of episodes of neutropenia after transplant

If there are sufficient number of patients with previous SCC in LT patients, incidence of recurrent SCC will be estimated among patients with history of SCC and the risk factors for recurrent SCC will be evaluated in univariate and multivariate analyses.

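### Voriconazole is classified ever/never while follow-up starts at transplant, so person-time before a later first dose counts as exposed and a true increase in SCC risk is understated

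*Protocol*

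**What the plan says.** - **Cohorts (Protocol 3.3).** Exposed: "Patients with LT who receive at least one dose of voriconazole regardless whether they also receive other antifungals will be included in this cohort". Unexposed: "Patients with LT who did not receive voriconazole will be included in this cohort". Neither definition is tied to the transplant date or to the date of an endpoint.
- **Time zero (3.5).** The index date is the date of transplant for all patients, and "The study eligible patients will be followed from the index date to whichever of the following occurs first": SCC or melanoma, death, last visit or 31 December 2012. Follow-up continues after one endpoint to look for the other.
- **Rates (7.2).** "Incidence rates of SCC of skin and melanoma by voriconazole exposed cohort and unexposed cohort will be calculated".
- **Primary model (7.3.1).** Under a heading that names the comparison of the two cohorts: "A univariate Cox proportional hazard regression analysis will be conducted to assess the association between voriconazole and SCC of skin". A multivariate Cox model follows. Section 7.3.2 uses a similar approach for melanoma.
- **Timing information.** Section 3.9.1 collects treatment start and stop dates, but names only duration as their use. It lists both prophylaxis and treatment of fungal infection as indications. Section 8 says that most patients receive an antifungal at the time of transplant, without a figure for voriconazole.

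**The concern.** Cohort membership is decided by something that may happen after follow-up has begun. A patient first dosed 18 months after transplant adds 18 undosed months to the exposed denominator. Those months carry the unexposed risk, so they dilute any real effect.

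How the dilution works depends on a point that section 3.3 leaves open:

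- **Reading A: a dose counts only if given before SCC.** The undosed time of an exposed patient is then SCC-free by construction. This is immortal time in the strict sense.
- **Reading B: any dose in the record counts, even after SCC.** This is the literal wording. The undosed time is then survived but not guaranteed SCC-free, and SCCs that preceded the drug can be attributed to it.

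This comparison is the primary objective of a safety study committed to the EMA. An error that shrinks a true harm works towards missing it. Adjusting for confounders does not return misallocated person-time to the right cohort.

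**Working it through.** **1. The plan's own figure.** Section 3.8 uses p0 = 5%, RR = 2.5 (so p1 = 12.5%), ratio 1:2, two-sided 5% and 80% power. The pooled proportion is (0.125 + 2 × 0.05)/3 = 0.075.

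n(exposed) = [1.960 × √(1.5 × 0.075 × 0.925) + 0.842 × √(0.125 × 0.875 + 0.05 × 0.95/2)]² / 0.075² = (0.632 + 0.307)² / 0.005625 ≈ 157, with 314 unexposed.

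The stated 157 and 314 reproduce and are not in dispute.

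**2. Inputs for the size of the bias**

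- From the protocol: p0 = 5%; one third exposed (1:2); transplants 2005-2008 with data to the end of 2012, hence 4 to 8 years of follow-up.
- Assumed: the 5% is reached at 5 years with constant hazard, λ = −ln(0.95)/5 = 0.0103 per year; death 10% per year; a share of users start late, with exponentially distributed delay; the others start at transplant.

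Cohorts of 2,000,000 were simulated and fitted with a fixed ever/never Cox model from transplant. Here f is the share of exposed person-time that falls before the first dose, shown for a true HR of 2.5.

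| Late starters, mean delay | f | True 2.5, reading A | True 2.5, reading B | True 1.0, reading A | True 1.0, reading B |
|---|---|---|---|---|---|
| none | 0 | 2.52 | 2.52 | 1.00 | 1.00 |
| 25%, 0.25 y | 0.014 | 2.45 | 2.48 | 0.97 | 0.99 |
| 25%, 1 y | 0.048 | 2.33 | 2.43 | 0.94 | 1.00 |
| 50%, 0.5 y | 0.054 | 2.30 | 2.41 | 0.93 | 1.01 |
| 50%, 1 y | 0.096 | 2.15 | 2.35 | 0.88 | 1.02 |
| 50%, 2 y | 0.145 | 2.00 | 2.27 | 0.81 | 1.00 |
| 100%, 1 y | 0.193 | 1.85 | 2.21 | 0.74 | 1.00 |

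Repeat runs moved single entries by up to about 0.03. Over all runs with late starters, a true 2.5 reads about 1.85-2.46 (A) or 2.2-2.5 (B), and a true 1.0 reads about 0.74-0.99 (A) or about 1.0 (B).

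**3. Check by hand, last row**

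- Reading B: the exposed rate is a person-time average, f × 1 + (1 − f) × 2.5 = 0.193 + 0.807 × 2.5 = 2.21, as simulated. At a true HR of 1.0 the same average is 1.0 whatever f is.
- Reading A: the exposed numerator loses the pre-dose SCCs, giving (1 − f) × 2.5 = 2.02. The further fall to 1.85 comes from the unexposed side, which keeps SCCs that occur before a planned dose but loses the undosed time of patients who reach their dose.

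**4. The remedy.** A Cox model with exposure switched on at the first dose gave 2.49-2.52 for a true 2.5 and 0.99-1.02 for a true 1.0 in the same scenarios.

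**5. Power, as a rough guide.** With 157 and 314 patients, the two-proportion power is 80% at RR 2.5, 71% at 2.3, 53% at 2.0 and 40% at 1.8.

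**6. Sensitivity to the hazard shape.** With a hazard that rises after transplant (Weibull shape 2, assumed; still 5% at 5 years) under reading A, 25% late at 1 year gives about 2.46 and 0.99. With 50% late at 1 year it gives about 2.38 and 0.95. The bias keeps its direction but is smaller.

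**The case against.** **The SAP may handle it.** Section 7 is expressly brief and refers to an SAP that is not shown. Section 7.3.1 does not say that voriconazole enters the Cox model as a fixed covariate. This stands as a caution about 7.3.1 alone. The cohort definition, time zero and the incidence rates by cohort are fixed in the protocol itself, and a time-dependent SAP analysis would depart from them. The further analytic methods mentioned in 7.3.1 are aimed at confounders, not at exposure timing.

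**Most users may start at transplant.** A reader might infer from the treatment indication in 3.9.1 that many first doses come long after transplant. The protocol does not say so. Its only timing statement, in section 8, leans towards early starts, although it concerns any antifungal, and a patient switched to voriconazole later still counts as exposed. Longer delays would produce larger attenuation than the table shows, but nothing in the protocol supports assuming them.

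**A drug without effect would look protective.** This is also tempting, but it needs reading A, which 3.3 does not state. Under the literal wording a null effect stays near 1.0.

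**The study as a whole is biased towards no harm.** This is not established either. Section 8 expects confounding by indication to link voriconazole with adverse outcomes, which may act in the opposite direction. Only this one component runs downward.

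**Conclusion.** The concern holds for the structure and for the direction of this bias. As written, time before a later first dose is counted as exposed in both the incidence rates and the Cox comparison, and nothing in the protocol corrects it. For a true harm the estimate is pulled down under either reading of the exposure definition.

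The size cannot be fixed from the protocol, because time to first dose is not given. It ranges from nil, if all users start at transplant, to a true 2.5 reading about 1.85, if all start late with a mean delay of one year and only doses before SCC count. These figures rest on the assumed delays, death rate and constant SCC hazard; a rising hazard makes the bias smaller. The point should be settled before analysis because it touches the primary objective and is cheap to remove.

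**What to change.** - **Section 3.3:** define voriconazole as a time-dependent exposure. A patient is unexposed from transplant to the first post-transplant dose and exposed from then on. State that a first dose after the endpoint being analysed is ignored, separately for SCC and melanoma.
- **Section 3.5:** keep transplant as time zero, with a cross-reference to this definition.
- **Section 7.2:** split person-years at the first dose and assign each SCC or melanoma to the exposure state at its date.
- **Section 7.3:** fit the Cox models in counting-process (start, stop] form with the same split, for both endpoints and for the voriconazole-only subgroup.
- **Baseline tables:** keep ever/never for description only.

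Cost: wording in the protocol and SAP and slightly more analysis work. The start dates are already collected under 3.9.1, so no new data or patients are needed.
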